**E) Population-level summary:**

- Primary (comparison vs fixed proportion):** Difference in proportion of participants with reduction of at least 2 log10 IU/mL in HBsAg levels from baseline at Week 24 using a fixed proportion of 2%.
- Secondary (comparison amongst regimens):** Difference in proportion of participants with reduction of at least 2 log10 IU/mL in HBsAg levels from baseline at Week 24 between study intervention arms.

**5.3.2.1. Main Estimator****5.3.2.1.1. Analysis Methods****5.3.2.1.1.1. Scientific Question of Interest Part a: Comparison vs Fixed Control**

The main estimator is constructed by using an exact binomial test against a fixed external control value of 2% at a one-sided Type 1 error rate of 0.05 and applying the Hochberg procedure for adjusting for multiple comparisons (Section 5.3.4).

### **5.3.2.1.1.2. Scientific Question of Interest Part b: Comparison Amongst Regimens**

The main estimator is constructed by using the Mantel-Haenszel test (Mantel N. et al., 1959) adjusted for the randomization stratification factors (HBsAg level at baseline [ $<1,000$  IU/mL,  $\geq 1,000$  IU/mL] and country grouping at enrollment [Poland, Russia, all other countries]) to compare the primary endpoint between the intervention arms at a one-sided alpha level of 0.05 and applying the Hochberg procedure for multiple comparisons adjustment.

### **5.3.2.1.2. Data Included**

The main analysis of the primary endpoint will be conducted using the FAS. The IFN-FAS and modified FAS/IFN-FAS analysis sets will be used if there is a relevant difference from the FAS ( $>5\%$  of participants in total).

Week 24 response status data from the selected population analysis set, after taking into account all the intercurrent events and applying the intercurrent event strategies in Section 5.3.2, will be included.

### **5.3.2.1.3. Assumptions**

- Missing Data for HBsAg are Missing Not at Random (MNAR)
- The treatment effect is homogeneous across strata

### **5.3.2.1.4. Missing Data Handling Rule**

Participants who withdraw from the study prior to Week 24 will be considered as non-responders.

If a participant remains in the study after experiencing a major protocol deviation (defined for the purpose of efficacy analyses and is an intercurrent event) and has missing Week 24 value, then the imputation to non-response will be applied. If the value for the endpoint at Week 24 is available, then such data will be used to determine their response status.

For the participants still in the study at Week 24 or for participants that have neither discontinued treatment early nor experienced any major protocol violations (defined for the purpose of efficacy analyses and is an intercurrent event), and HBsAg values missing at Week 24, then the primary method to handle missing data will be the missing as non-responder (MANR).

## **5.3.2.2. Sensitivity Estimators of the Main Estimand**

Sensitivity analyses will be conducted by constructing three sensitivity estimators for the main estimand as defined in Section 5.3.2.

### **5.3.2.2.1. Sensitivity Estimator 1 of the Main Estimand (Homogeneity Assumption)**

Homogeneity will be assessed for scientific question of interest part b, comparison amongst regimens. For this sensitivity estimator 1, the same included data, missing data assumption, and missing data handling rule (MANR) as well as the same approach to control the Type I error rate (Section 5.3.2.1) will be applied. The assumption for homogeneity of treatment effect across the

stratification factors will be tested and, if heterogeneity is found statistically significant, a different statistical model is used to define the sensitivity estimator.

#### **5.3.2.2.1.1. Assumptions**

- Missing Data for HBsAg are Missing Not at Random (MNAR)
- The treatment effect is non-homogeneous across strata

#### **5.3.2.2.1.2. Analysis Methods**

Homogeneity of treatment effect for each stratification factor separately will be tested using the weighted least squares chi-squared statistic (Lui K. J. et al., 2000) for one-way homogeneity. Tests of homogeneity will be assessed at the one-sided 10% level of significance.

Any heterogeneity found to be statistically significant will be explored using the following statistical model.

**Statistical model:** A logistic regression model on the primary efficacy endpoint using the 2 randomization stratification factors and interaction terms. The model will include intervention arm, HBsAg level at baseline ( $<1,000$  IU/mL or  $\geq 1,000$  IU/mL), and country grouping at enrollment (Poland, Russia, all other countries) as factors, and the intervention arm-by-factor interaction terms.

#### **5.3.2.2.2. Sensitivity Estimator 2 of the Main Estimand (Observed Case Analysis)**

For this sensitivity estimator 2, the same statistical model, and data included will be used as for the main estimator (Section 5.3.2.1). The assumption for missing data and the rule to handle missing data have changed.

##### **5.3.2.2.2.1. Assumptions**

- Missing Data for HBsAg are Missing Completely at Random (MCAR) (Barnes A. et al., 2008)
- The treatment effect is homogeneous across strata

##### **5.3.2.2.2.2. Missing Data Handling Rule**

For sensitivity estimator 2, participants who withdrew from the study prior to Week 24 will not be included in the analysis. After taking into account all the intercurrent events and applying the intercurrent event strategies specified in Section 5.3.2, if a subject who did not experience any ICEs has missing response status for the primary endpoint then this participant will not be used for the analysis.

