**D) Intercurrent events:**

- Treatment discontinuation prior to Week 24: if the participant discontinued treatment prior to Week 24 then s/he will be considered non-responder (composite strategy).
- Major protocol deviations affecting efficacy: Table 13 identifies the deviations considered intercurrent event. Participants with such deviations and who have missing data for the endpoint will be considered as non-responders (composite strategy). For all other deviations not considered intercurrent events, the data are used regardless of the occurrence of major protocol deviations (treatment policy strategy).
- Deaths prior to Week 24 are handled in a composite strategy as participants who die prior to Week 24 will be considered as non-responders.

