### 5.3.2.2.3.2. Missing Data Handling Rule

For sensitivity estimator 3, participants who withdraw from the study prior to Week 24 will be considered as non-responders. After taking into account all the intercurrent events and applying the intercurrent event strategies specified in Section 5.3.2, if a subject who did not experience any ICEs has missing response status for the primary endpoint then the LOCF approach will be used as follows.

If the HBsAg value at Week 24 is missing, the non-missing closest to Week 24 within the window of 4 weeks prior/after Week 24 visit will be used. If 2 non-missing laboratory values are equidistant, the later observation will be preferred. Participants who do not have data within the analysis window of  $\pm 4$  weeks around Week 24 assessment will be defined as non-responders.

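### Sensitivity estimator 2 removes participants whom the main estimand already counts as failures, so it is not a sensitivity estimator of that estimand

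*SAP*

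**What the plan says.** SAP 5.3.2, item D, defines the intercurrent events of the main estimand. For treatment discontinuation the rule is "if the participant discontinued treatment prior to Week 24 then s/he will be considered non-responder (composite strategy"). For death it is that "participants who die prior to Week 24 will be considered as non-responders". Study withdrawal is not listed there. It appears in the main estimator's missing-data rule (5.3.2.1.4): "Participants who withdraw from the study prior to Week 24 will be considered as non-responders". The data for the main estimator (5.3.2.1.2) are Week 24 response statuses that, "after taking into account all the intercurrent events and applying the intercurrent event strategies in Section 5.3.2, will be included".

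SAP 5.3.2.2 describes all three sensitivity estimators as estimators of the main estimand. For estimator 2, the observed-case analysis, 5.3.2.2.2 says "the same statistical model, and data included will be used as for the main estimator"; only the assumption about missing data (now MCAR) and the handling rule are said to change. That rule (5.3.2.2.2.2) has two sentences. The first is: "participants who withdrew from the study prior to Week 24 will not be included in the analysis". The second begins "After taking into account all the intercurrent events and applying the intercurrent event strategies specified in Section 5.3.2" and then drops only participants who had no intercurrent event and whose response status is missing.

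Estimator 3 (5.3.2.2.3.2), which also assumes MCAR, keeps the main rule: "participants who withdraw from the study prior to Week 24 will be considered as non-responders".

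SAP 1.2 schedules the last JNJ-3989 dose at Week 24 for every participant. It sends those who stop JNJ-3989 early into follow-up unless they withdraw consent.

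**The concern.** Under the composite strategy, a participant who stops treatment before Week 24 has a known outcome: failure. Leaving the study before Week 24 implies missing the Week 24 JNJ-3989 dose, so an early withdrawal is also an early treatment discontinuation or a death. Estimator 2 removes such a participant as though the outcome were unknown.

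Like cases are then handled differently. Someone who stops JNJ-3989 early and stays for follow-up is a failure, even with a Week 24 HBsAg value. Someone who stops and leaves disappears from numerator and denominator. The remaining quantity is response among those who stayed in the study.

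The stake is interpretation. If estimator 2 differs from the main result, the reader cannot separate an effect of missing data from an effect of the changed estimand. The distortion is largest where withdrawal is highest. The arms differ in PegIFN-α2a duration and timing, so unequal withdrawal is possible, though neither document predicts it.

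**Working it through.** **Plan's own figures.** SAP 3 gives 30 per arm, about 10% attrition, 34 per arm and 102 in total. 30/(1 − 0.10) = 33.3, rounded up to 34, and 3 × 34 = 102: reproduced. Power above 95% for 32% against 2% at n = 30 also reproduces: 99.9% at one-sided 0.05 (at least 3 responders) and 99.5% at 0.05/3 (at least 4). The sample size is not in dispute.

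**How a participant who leaves before Week 24 is scored**

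| Place in SAP | Result |
|---|---|
| 5.3.2 D, through treatment discontinuation or death | non-responder |
| 5.3.2.1.4, main estimator | non-responder |
| 5.3.2.2.3.2, estimator 3 | non-responder |
| 5.3.2.2.2.2, second sentence taken alone | non-responder |
| 5.3.2.2.2.2, first sentence | removed |

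**Effect on one arm.** Let n = 34, w = withdrawals before Week 24 and r = responders. With withdrawals as failures the rate is r/34; with withdrawals removed it is r/(34 − w). The ratio is 34/(34 − w) = 1/(1 − w/34). Other missing data are ignored.

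- w = 3 (3/34 = 8.8%, the whole number nearest 10%), r = 17: 17/34 = 50.0% and 17/31 = 54.8%, up 4.8 points.
- w = 3, r = 27: 27/34 = 79.4% and 27/31 = 87.1%, up 7.7 points.
- w = 4 (the margin 34 − 30, or 11.8%), r = 15: 15/34 = 44.1% and 15/30 = 50.0%, up 5.9 points.
- Assumed range w = 1 to 7: at r = 17 the increase runs from 1.5 points (17/33 = 51.5%) to 13.0 points (17/27 = 63.0%). At r = 27 it runs from 2.4 points (27/33 = 81.8%) to 20.6 points (27/27 = 100%).

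**Effect on a comparison of two arms.** These splits are assumptions, not document values. Take 17 responders in each arm, so that with withdrawals as failures the comparison is 50% vs 50%, and 8 withdrawals in total.

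- 4 and 4: 17/30 vs 17/30, no difference.
- 5 and 3: 17/29 = 58.6% vs 17/31 = 54.8%, 3.8 points.
- 6 and 2: 17/28 = 60.7% vs 17/32 = 53.1%, 7.6 points in favour of the arm that lost more participants.

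**Effect against the fixed 2%.** Exact one-sided p-values at n = 34 and n = 31 are 0.148 and 0.127 for 2 responders, 0.030 and 0.024 for 3, and 0.0046 and 0.0033 for 4. The Hochberg steps are 0.05, 0.025 and 0.0167. With three withdrawals, a step is crossed only at exactly 3 responders (3/34 = 8.8%), far below the 32% used for power.

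**The case against.** Study withdrawal is not one of the listed intercurrent events. The SAP places the withdrawal rule under missing-data handling, and 5.3.2.2.2 announces that this handling changes. The two sentences of 5.3.2.2.2.2 can therefore be read in order: remove withdrawals, then apply the intercurrent-event strategies to those who remain. The analysis is openly titled observed case and states MCAR. It is also the only sensitivity estimator that varies how withdrawals are handled.

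Much of this stands. A reader might infer that 5.3.2.2.2.2 contradicts itself; the sequential reading removes that literal clash. A reader might also treat the disagreement with estimator 3 as a defect in itself. It is not, because sensitivity analyses are meant to use different missing-data rules. Nor is the analysis uninformative: the same conclusion with withdrawals as failures and with withdrawals removed says something about how much withdrawal handling matters.

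The sequential reading does not rescue the label. It still removes participants whom 5.3.2 D defines as failures. It does not fit the statement that the included data match those of the main estimator, which are response statuses after the intercurrent-event strategies. MCAR does not explain the exclusion either, since estimator 3 makes the same assumption and keeps withdrawals as failures.

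**Conclusion.** The point holds, with limited reach. As written, estimator 2 estimates response among participants who stayed in the study and should not be called a sensitivity estimator of the main estimand. This rests on one inference: withdrawal before Week 24 entails early treatment discontinuation or death, because dosing runs to Week 24.

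The inflation is 4.8 points for 17 responders at 3 of 34 withdrawn, and larger with more responders or more withdrawals. The attrition in SAP 3 is not defined as withdrawal before Week 24, so these withdrawal counts are assumptions. Four of 34 is 11.8%, not the planned 10%.

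A reader might infer that the rule will favour Arm 1, which has the longest PegIFN-α2a exposure. The documents give no withdrawal rates by arm, so the 6-versus-2 case is illustration only. A reader might also infer that the primary conclusion is at risk. It is not: the main estimator is untouched, and the effect of this rule against the fixed 2% is negligible. What is exposed is the secondary between-arm comparison in this one sensitivity analysis.

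**What to change.** Choose one of two repairs, before database lock.

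1. In SAP 5.3.2.2.2.2, replace the first sentence with the rule of 5.3.2.1.4 and 5.3.2.2.3.2, so that withdrawals before Week 24 are non-responders. Exclude only participants with no intercurrent event whose Week 24 HBsAg is missing. This is a one-sentence change. Estimator 2 would then differ from the main estimator only for that small group, and no sensitivity estimator would vary the handling of withdrawals.

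2. Keep the exclusion, but move the analysis out of 5.3.2.2 and label it a supplementary estimand among participants who stayed in the study to Week 24. Remove the claim that its included data match those of the main estimator, and report withdrawals by arm beside it. This costs a short estimand description.

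Under either repair, state explicitly that deaths before Week 24 remain non-responders even if recorded as study withdrawals. Neither option needs new data or a change in sample size.

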#### **5.3.2.2.3. Sensitivity Estimator 3 of the Main Estimand (LOCF)**

For this sensitivity estimator 3, the same statistical model, and data included will be used as for the main estimator (Section 5.3.2.1). The assumption for missing data and the rule to handle missing data have changed.

### 5.3.2.2.3.1. Assumptions

- Missing Data for HBsAg are MCAR (Barnes A. et al., 2008)
- The treatment effect is homogeneous across strata

### 5.3.2.2.3.2. Missing Data Handling Rule

For sensitivity estimator 3, participants who withdraw from the study prior to Week 24 will be considered as non-responders. After taking into account all the intercurrent events and applying the intercurrent event strategies specified in Section 5.3.2, if a subject who did not experience any ICEs has missing response status for the primary endpoint then the LOCF approach will be used as follows.

If the HBsAg value at Week 24 is missing, the non-missing closest to Week 24 within the window of 4 weeks prior/after Week 24 visit will be used. If 2 non-missing laboratory values are equidistant, the later observation will be preferred. Participants who do not have data within the analysis window of  $\pm 4$  weeks around Week 24 assessment will be defined as non-responders.

## 5.3.3. Supplementary Estimand for the Primary Endpoint (Per-Protocol Analysis Set)

### A) Study Intervention:

- Arm 1: JNJ-3989 for 24 weeks + NA for 24 weeks + PegIFN- $\alpha$ 2a for 24 weeks.
- Arm 2: JNJ-3989 for 24 weeks + NA for 24 weeks + PegIFN- $\alpha$ 2a from Week 12 till Week 24.
- Arm 3: JNJ-3989 for 24 weeks + NA for 24 weeks + PegIFN- $\alpha$ 2a from baseline till Week 12.

**B) Study Population:** HBeAg-negative chronic HBV-infected adult patients who are virologically suppressed by being treated with NA.

**C) Variable:** Response status defined as participants with reduction of at least 2 log10 IU/mL in HBsAg levels from baseline at Week 24 (responders) as in Section 5.3.1.

### D) Intercurrent events:

- Treatment discontinuation prior to Week 24: if the participant discontinued treatment prior to Week 24 then s/he will be considered non-responder (composite strategy).
- Deaths prior to Week 24 are handled in a composite strategy as participants who die prior to Week 24 will be considered as non-responders.

### E) Population-level summary:

- a. Primary (comparison vs fixed proportion):** Difference in proportion of participants with reduction of at least 2 log10 IU/mL in HBsAg levels from baseline at Week 24 using a fixed proportion of 2%.

- b. Secondary (comparison amongst regimens):** Difference in proportion of participants with reduction of at least 2  $\log_{10}$  IU/mL in HBsAg levels from baseline at Week 24 between study intervention arms.

### 5.3.3.1. Main Estimator of the Supplementary Estimand

#### 5.3.3.1.1. Analysis Methods

Similar methods as described for the main estimator of the main estimand will be used (Section 5.3.2.1.1).

#### 5.3.3.1.2. Data Included

Week 24 response status data from randomized participants that are included in the PP analysis set will be used, after taking into account the intercurrent events and applying the intercurrent event strategies specified in Section 5.3.3.

To complement this analysis because of its inherent bias and allow a better interpretation of the results, the proportions of participants excluded from the PP analysis set will be summarized by intervention arm and by type of major protocol deviation.

#### 5.3.3.1.3. Assumptions

- Missing Data for HBsAg are MANR
- The treatment effect is homogeneous across strata.

#### 5.3.3.1.4. Missing Data Handling Rule

Participants who withdraw from the study prior to Week 24 will be considered non-responders. For the participants still in the study at Week 24 or for participants that have neither discontinued treatment early nor experienced any major protocol violations as listed at Table 13, but HBsAg values missing at Week 24, then the primary method to handle missing data will be the imputation to non-responder.

### 5.3.4. Hochberg Procedure

Consider testing the family of hypotheses  $H_{0i}$ ,  $i = 1, \dots, k$ .

Let  $p_i$ ,  $i = 1, \dots, k$ , denote the sample p-values of tests for  $H_{0i}$ ,  $i = 1, \dots, k$ , computed without multiplicity adjustment. Let  $[1], \dots, [k]$  denote the random indices such that

$$p_{[1]} \leq \dots \leq p_{[k]}.$$

That is,  $[i]$  is the anti-rank of  $p_i$  among  $p_1, \dots, p_k$ .

Hochberg's step-up method proceeds as follows.

Step 1. If  $p_{[k]} < \alpha$ , reject  $H_{0[i]}$ ,  $i = 1, \dots, k$ , and stop; otherwise go to Step 2.

Step 2. If  $p_{[k-1]} < a/2$ , reject  $H_{0[i]}$ ,  $i = 1, \dots, k - 1$ , and stop; otherwise go to Step 3.

...

Step k. If  $p_{[1]} < a/k$ , reject  $H_{0[i]}$ ,  $i = 1$ , and stop.

### 5.3.5. Subgroup Analyses of Primary Efficacy Endpoint

The potential association between the primary endpoint and the randomization stratification factors will be assessed by a logistic regression model (Brooks ST. et al., 2004) and exploration of the interaction terms using observed case data. The model will include intervention arm, country grouping as proxy for HBV genotype at enrollment (Poland (predominantly GT-A) vs Russia (predominantly GT-D) vs all other countries (other or mixed GT prevalence)), absolute HBsAg value at baseline (<1,000 IU/mL vs  $\geq 1,000$  IU/mL), as factors, and the interaction of intervention arm-by-country grouping, and intervention arm-by-HBsAg value at baseline as interaction terms. The primary endpoint estimates for each intervention arm will be derived from this model and presented graphically with their 90% CI in a forest plot.

In addition, for assessment of internal consistency and investigation of homogeneity of the treatment effect in the primary efficacy endpoint across other subgroups (as defined in Section 5.7.7.1), similarly to what is described above, a logistic regression model (Brooks ST. et al., 2004) will be estimated for each subgroup variable at a time. The factors in the model will be intervention arm, the subgroup variable, and the two randomization stratification factors (country grouping as proxy for HBV genotype at enrollment [Poland (predominantly GT-A) vs Russia (predominantly GT-D) vs all other countries (other or mixed GT prevalence)], absolute HBsAg value at baseline [ $<1,000$  IU/mL vs  $\geq 1,000$  IU/mL]), and the intervention arm-by-subgroup interaction term. Corresponding 90% CIs will be also calculated without multiplicity adjustment for each intervention arm. Statistical analysis of treatment heterogeneity between subgroups will be conducted by assessing the significance of the interaction term (Brooks ST. et al., 2004). The forest plot will present graphically the primary endpoint estimate, its 90% CI resulting from the model across intervention arms by the prespecified subgroups.

The primary efficacy endpoint will be summarized also descriptively using the number and percentage of participants in each intervention arm, by each subgroup of interest (Section 5.7.7.1). In addition, the tabulation of count and percentage of responders will be calculated for the combination of the 2 randomization stratification factors of country grouping-by-HBsAg at baseline categories.

### 5.3.6. Comparisons Between Arm 2 and Model-Based Virtual IFN-Free JNJ-3989+NA Regimen Control

As study participants were not randomized across those ISAs ongoing at the time of writing this SAP, because of the staggered ISAs initiation, any imbalance in baseline characteristics, beyond matching the key inclusion/exclusion criteria, may introduce potential bias in the treatment effect estimation. Such additional sources of variability could be driven by country effect, HBV genotype, time effect (e.g. time of the participant's enrollment into an ISA), impact of the COVID-

19 pandemic on protocol compliance, as well as by the different combination regimens and the different JNJ-3989 treatment durations across ISAs. To address these concerns another analysis of the primary efficacy endpoint will be performed constructing “virtual” IFN-free JNJ-3989 control participants for the participants in this ISA (Arm 2). Virtual control HBsAg data are defined as IFN-free regimen with JNJ-3989+NA, at the JNJ-3989 dose level used in this ISA. For each participant in Arm 2 of this ISA, the HBsAg data for “virtual” control subjects will be generated using an appropriate longitudinal model (e.g. kinetic pharmacodynamic model [KPD] or PK/PD model) developed and validated based on the data from the JNJ73763989HPB2001 (REEF-1) study. In Arm 2, the first 12 weeks of HBsAg data under treatment with JNJ-3989+NA alone will enable to estimate individual parameters (ie, Empirical Bayes Estimates) describing each participant’s specific HBsAg temporal kinetics. These individual parameters will be used further to extrapolate each participant’s individual HBsAg values over time, as if that participant had been treated with JNJ-3989 +NA regimen but without receiving PegIFN- $\alpha$ 2a for the entire 24-week treatment. The observed HBsAg levels post PegIFN- $\alpha$ 2a intake in Arm 2 will be directly compared to virtual control model-generated HBsAg data for this arm. Of Note: the model-based prediction of HBsAg between weeks 12-24 for each individual in Arm2 assumes that (i) the individual’s HBsAg dynamics follow the general path of the population-level HBsAg turnover model, and (ii) assumes absence of immune-related effects.

***Single-arm estimate of the primary endpoint response rate (study intervention arm and virtual control-arm):*** The estimated primary endpoint response rate will be calculated for the virtual control arm, and 90% CI will be estimated using Clopper-Pearson exact method for a single sample proportion. The same Clopper Pearson method will also apply to estimate the 90% CI around the response rate for the Arm 2 of this ISA.

***Matched-control paired difference in the primary endpoint response rate (study intervention arm vs. virtual control-arm):*** The proportion of responders estimated for participants in this ISA will be compared with the proportion of responders obtained for the virtual IFN-free JNJ-3989 control participants model-generated using the McNemar test for the difference between paired matched case-control binomial proportions at 0.05 one-sided Type 1 error rate. The associated 90% CI will be estimated to accompany the point estimate of the difference in proportions.

No multiplicity adjustment will be used in this exploratory statistical comparison.

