9.4.2.3. Across ISAs Comparisons of Efficacy

Indirect comparisons between different regimens across multiple ISAs will be performed in an exploratory fashion by selecting the similar subgroup of participants who match the most important inclusion/exclusion criteria and demographic characteristics of this ISA, such as for example the virologically suppressed participants who are HBeAg negative at screening across 73763989PAHPB2007 (this ISA), [73763989PAHPB2002 \(REEF-2\)](#), and [73763989PAHPB2006 \(PENGUIN\)](#) ISAs.

To further evaluate the impact of potential differences between ISAs, a virtual control arm will be generated for this ISA. Virtual control efficacy data will be defined as IFN-free regimen with JNJ-3989+NA at the dose level used in this ISA. Creating a virtual control arm by fitting the PK/PD model to the available HBsAg data can be performed for subjects with serum HBsAg >100 IU/mL at screening. The same approach may also be considered for subjects with serum HBsAg ≤100 IU/mL at screening, but as these subjects were typically not included in previous JNJ-3989 studies, the feasibility of this approach will be assessed based on the current analysis results.

For each participant in Arm 2 of this ISA, the HBsAg data for “virtual” control subjects will be generated using an appropriate longitudinal model (eg, kinetic pharmacodynamic model [KPD] or PK/PD model) developed and validated based on the data from the [73763989HPB2001 \(REEF-1\)](#) study. In Arm 2, the first 12 weeks of HBsAg data under treatment with JNJ-3989+NA alone will enable to estimate individual parameters (ie, Empirical Bayes Estimates) describing each participant's specific HBsAg temporal kinetics. These individual parameters will be used further to extrapolate each participant's individual HBsAg values over time, as if that participant had been treated with JNJ-3989+NA regimen (matching the same JNJ-3989 dose level) but without receiving PegIFN-α2a treatment. The observed HBsAg levels post PegIFN-α2a intake in Arm 2 will be directly compared to virtual control model-generated data for this arm. Due to the randomization, the virtual control subjects derived for Arm 2 can be considered exchangeable with the participants of the other arms in this ISA. Therefore, the estimates of HBsAg efficacy endpoints at the group level of the virtual control subjects for Arm 2 will also be compared to the other arms in this ISA.

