##### **5.4.2.1. Binary Endpoints**

All binary endpoints defined using HBsAg values/changes from baseline (HBsAg cut-offs, HBsAg seroclearance/seroconversion, Functional Cure) will be analyzed also using the virtual control approach described in Section 5.3.6.

For single arm point and 90% CI estimates, the Clopper Pearson method will be used. For the difference between paired matched case-control binomial proportions, the McNemar test at 0.05 one-sided Type 1 error rate will be used.

Graphical displays using bar charts and/or radar plots will show the binary endpoints over time, by subgroups of interest, or combining multiple binary endpoints together.

Potential association between treatment outcome and baseline factors will be explored by multivariate logistic regression model in a similar fashion as described in Section 5.3.5.

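### The exploratory virtual-control comparison analyses model-predicted response as if it were observed, so its nominal 5% level and 90% CI do not hold in general, and it covers two endpoints an HBsAg model cannot produce

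*SAP*

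**What the plan says.** SAP 5.3.6, following Protocol 9.4.2.1 and 9.4.2.3, builds an IFN-free virtual control for Arm 2. A longitudinal HBsAg model developed on REEF-1 is combined with "the first 12 weeks of HBsAg data under treatment with JNJ-3989+NA alone". According to the SAP, this early run of values "will enable to estimate individual parameters (ie, Empirical Bayes Estimates) describing each" person's HBsAg kinetics. Those estimates are extrapolated to Week 24.

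Three inferential steps follow:

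- For the virtual arm's response rate, "90% CI will be estimated using Clopper-Pearson exact method for a single sample proportion".
- Observed and virtual response are compared, the virtual side being "model-generated using the McNemar test for the difference between paired matched case-control binomial proportions at 0.05 one-sided Type 1 error rate".
- An interval for the paired difference is promised ("The associated 90% CI will be estimated to accompany the point estimate of the difference in proportions"), but no method is named for it.

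The SAP discloses two model assumptions: each individual follows the population HBsAg path, and there are no immune-related effects. It labels the comparison exploratory and unadjusted.

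SAP 5.4.2.1 then carries the approach to secondary binary endpoints: "HBsAg cut-offs, HBsAg seroclearance/seroconversion, Functional Cure) will be analyzed also using the virtual control approach". On scope, Protocol 9.4.2.3 says the virtual arm "can be performed for subjects with serum HBsAg >100 IU/mL at screening" and leaves feasibility at or below 100 IU/mL to be assessed. SAP 5.3.6 does not repeat that condition.

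**The concern.** McNemar's test and the Clopper-Pearson interval assume observed binary outcomes that are independent between pairs or participants. McNemar's null hypothesis also requires equal response rates on the two sides when PegIFN adds nothing. A prediction differs from an observation in three ways:

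- Error in the REEF-1 population parameters moves all virtual controls together, so they are not independent.
- An individual prediction omits the part of the Week 24 decline that 12 weeks of data cannot foresee, and it omits residual error.
- Empirical Bayes estimates shrink towards the population mean. Predicted declines are therefore less spread out than real ones, and the share beyond 2 log10 is biased unless the typical decline sits at the threshold.

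If these are ignored, model error alone can show or hide a PegIFN effect. Protocol 9.4.2.3 also compares the virtual-arm estimates with the other two arms, so an error would carry over to them.

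**Working it through.** **1. What the plan gives.** The documents state no power or error calculation for this comparison; 0.05 is only a nominal level. Usable inputs are 34 participants in Arm 2 and the 50% planning response rate derived from REEF-1 (both SAP 3). As a benchmark, with two genuinely observed, exchangeable outcomes and 34 pairs, simulation gives one-sided type I error of 4.8-5.0% for asymptotic McNemar and 1.5-1.8% for the exact version. The SAP does not say which it means. The test is therefore sound for real data, and any departure below comes from using predictions.

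**2. Assumptions not in the documents.** IFN-free Week 24 decline has mean μ and SD σ = 0.5 log10. A share R² of 50-70% of its variance is predictable at Week 12. A model error with standard error τ is shared by all virtual controls. PegIFN has no effect.

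**3. Bias from shrinkage alone (τ = 0).**

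- Observed rate = 1 − Φ((2 − μ)/σ).
- Virtual rate = 1 − Φ((2 − μ)/(σ√R²)).

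At μ = 1.8:

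- observed 1 − Φ(0.2/0.5) = 1 − Φ(0.40) = 34.5%
- virtual, R² = 0.5: 1 − Φ(0.2/0.354) = 1 − Φ(0.566) = 28.6%
- virtual, R² = 0.7: 1 − Φ(0.2/0.418) = 1 − Φ(0.478) = 31.6%

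The gap is 3 to 6 percentage points in favour of PegIFN. At μ = 2.2 it is the mirror image (observed 65.5%, virtual 68.4-71.4%). At μ = 2.0 both rates are 50% and there is no gap.

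**4. Effect of a shared error.** At μ = 2.0 a shift of 0.10 log10 moves the virtual rate by Φ(0.10/0.354) − 0.5 = 11 points (R² = 0.5) or Φ(0.10/0.418) − 0.5 = 9 points (R² = 0.7). The sampling SE of the paired difference in this model is 7-9 points, so the unmodelled error is as large as the modelled one.

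**5. Simulation (40,000 trials per setting, 34 pairs, McNemar z > 1.645).**

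| Mean decline | Shared SE (log10) | One-sided type I error | 90% CI coverage |
|---|---|---|---|
| 1.8 | 0 | 10-18% | – |
| 2.0 | 0 | about 5% | – |
| 2.0 | 0.10 | 15-16% | about 65% |
| 2.0 | 0.15 | 21-22% | about 53% |
| 2.2 | 0 | 1-2% | – |

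**6. A second set of assumptions.** With SD 0.6, residual SD 0.15, R² of 0.5-0.9, shared SD 0-0.3 log10 and response rates of 30-70% (4,000 trials per setting), type I error ran from 0.4% to 38% and naive CI coverage from 36% to 89%. At the plan's 50% response rate, shared SDs of 0.1, 0.2 and 0.3 gave about 12%, 23-24% and 29-30%, with coverage of about 72%, 48% and 37%.

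**7. Endpoints.** SAP 5.4.1.1.7 defines seroconversion as seroclearance plus appearance of anti-HBs. SAP 5.4.1.1.5 defines functional cure as seroclearance at FU Week 12, 24, 36 or 48 without NA re-treatment being required since Week 24. The model in SAP 5.3.6 yields HBsAg only, and its assumptions are stated only for Weeks 12-24. It produces neither anti-HBs nor NA re-treatment status. HBsAg cut-offs and quantitative seroclearance can in principle be derived from it.

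**8. Discontinuation.** SAP 5.3.2 counts observed discontinuation before Week 24 as non-response; no counterpart is stated for virtual values. As an illustration, 10% discontinuation (the attrition figure in SAP 3) at a 50% response rate lowers the observed rate by 0.10 × 0.50 = 5 points. With a perfect population model, that takes rejection to about 1%.

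**The case against.** The strongest reply is that this is a disclosed, exploratory analysis outside the primary test against 2% and its Hochberg family, and that modelling detail is deferred to another document (SAP 1, Protocol 9.4.2.3). That limits the consequence. It does not remove the point, because the SAP itself fixes the inference (Clopper-Pearson and McNemar at 0.05) and a modelling plan alone would not change that. The SAP does not state whether residual error or repeated draws enter the predictions, so a single point prediction is the natural reading rather than an explicit statement.

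A second reply is that the size rests on assumed SDs and that the level is nominal at 50% response with a perfect population model. Both are correct. The figures show a risk and a range; they do not measure this trial.

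A reader might also infer three stronger things that the documents do not support:

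- *This is the trial's only estimate of what PegIFN adds.* It is not. Until Week 12, Arms 1 and 3 receive PegIFN and Arm 2 does not, which is a randomised, concurrent contrast. The SAP analyses HBsAg by arm over time (5.4.2.1.4, 5.4.2.2.1). Comparisons with REEF-2 and PENGUIN are also planned. The virtual control is the only within-trial IFN-free estimate at Week 24.
- *The test always overstates PegIFN.* The direction depends on where the typical decline lies relative to 2 log10 and on the sign of the model error.
- *The SAP contradicts the protocol on HBsAg above 100 IU/mL.* Protocol 9.4.2.3 also refers to each participant in Arm 2 and allows the approach at or below 100 IU/mL subject to feasibility. The SAP omits that caveat; it does not reverse it.

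**Conclusion.** The concern holds in this form. As specified, the virtual-control comparison makes no allowance for prediction error, so its one-sided 0.05 level and 90% CI are not assured. Under the first set of assumptions, type I error runs from 1-2% to 21-22%; over the second, wider grid it runs from 0.4% to 38%, with CI coverage below 90% throughout. It is about nominal only near 50% response with an accurate population model. These sizes rest on variances and model-error SDs that the documents do not give.

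The endpoint problem needs no assumptions: seroconversion and functional cure cannot be generated from the model described. The primary analysis is unaffected. What is at stake is the credibility of the Week 24 IFN-free comparison.

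**What to change.** 1. In SAP 5.3.6, replace McNemar and the virtual-arm Clopper-Pearson interval. For each Arm 2 participant, draw the Week 24 value repeatedly from the posterior predictive distribution, covering population-parameter, individual and residual error. Report the mean paired difference with a 90% interval that combines prediction and sampling error. An illustration of this kind (40 draws combined by Rubin's rules, on the grid in step 6) gave type I error of 0.1-5.8% and coverage of 89-99.8%.
2. State that draws do not remove a fixed model bias, and add a sensitivity analysis shifting the predicted IFN-free decline over a stated range, for example 0.1-0.3 log10. In the same illustration at 50% response, under-predicting the decline by 0.1, 0.2 and 0.3 log10 still gave 3.9%, 22% and 58% type I error, against 25%, 63% and 90% for the planned test.
3. Remove seroconversion and functional cure from the virtual-control list in SAP 5.4.2.1.
4. Carry the protocol's feasibility condition for screening HBsAg at or below 100 IU/mL into SAP 5.3.6.
5. Do not copy discontinuations to the virtual values: that would cancel PegIFN-caused discontinuation, which the composite estimand counts. Report the comparison both with observed discontinuations as non-response and among participants with an observed Week 24 value.

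The cost is SAP wording, modelling time and a wider interval. That interval may be conservative when the population model is accurate (0.1-0.4% type I error in the illustration with no shared error).
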